6.4.8. Clinical Laboratory Tests

Clinical safety laboratory tests are to be performed by the local laboratory as outlined in the Schedule of Assessments and patients are to be fasting for 8 hours. Labs are to be drawn prior to dosing.

All clinically significant laboratory abnormalities will be followed-up by repeat testing and further investigated according to the judgment of the Investigator.

Liver function test abnormalities will be evaluated in accordance with FDA Guidance (2009) as described in the [Appendix 11.8](#).

Specific tests are described below.

6.4.8.1. Hematology Clinical Chemistry and Urinalysis

Hematology:

Complete blood count with platelet count and standard indices will be obtained.

Chemistry:

Sodium, potassium, chloride, CO₂, albumin, total protein, glucose, blood urea nitrogen (BUN), creatinine, uric acid, aspartate aminotransferase (AST), alanine aminotransferase (ALT), gamma-glutamyltranspeptidase (GGT), creatine phosphokinase (CPK), alkaline phosphatase, total bilirubin, direct bilirubin, lactate dehydrogenase (LDH), calcium and phosphorus.

Urinalysis:

pH, glucose, protein, ketones, bilirubin, blood, urobilinogen, specific gravity, nitrite, and leukocytes by dipstick analysis or machine urinalysis. Urine microscopic examination will be performed if positive findings on dipsticks warrant further examination.

6.4.8.2. Serum Samples for Storage

Extra retain samples will be taken pre-dose prior to double-blind study drug, and at the end of the 4-week double blind treatment period and will be used only in the event that unscheduled diagnostic tests are required for safety reasons, or for [REDACTED] that are currently not defined but are directly related to the aims of this study. These samples will be retained until the study

has been completed, and until the Sponsor has notified the study site in writing that the samples can be discarded.

6.4.9. Injection Site Evaluation and Scoring

Injection sites will be carefully inspected, evaluated and scored during the study period. The injection site evaluation will include identification and measurement of areas of erythema, edema and induration, as well as the presence of localized pain, tenderness and itching. A sample injection site evaluation form is included in the [Appendix](#).

Injection site evaluations and scoring will be conducted according to the SOA. In addition, unscheduled evaluations may also be recorded as warranted by clinical conditions.

6.4.10. Anti-RM-493 Antibody Measurements

Blood samples for measurement of anti-RM-493 antibodies will be drawn pre-dose, and thereafter according to the SOA.

6.4.11. Patient Questionnaires

The patient questionnaires will be answered by the patient and/or caretaker after careful training.

PWS Hyperphagia Questionnaire (Dykens, 2014)

[figure not shown]
The PWS Hyperphagia Questionnaire is a tool for assessing hyperphagia-related behavior and will be a primary endpoint of the study, evaluated at both the end of the 4-week double-blind treatment phase, and again at the end of the 2-week randomized double-blind withdrawal phase.

Food Related Problems Questionnaire (Russell 2003)

The Food-Related Problems Questionnaire is a tool specifically designed for patients with Prader-Willi Syndrome to rate preoccupation with food, impairment of satiety, difficulty with self-control and other food-related 'challenging' behavior.

[REDACTED]

[REDACTED]

6.4.12. Diet and Behavior Training and Counseling

No special dietary counseling will be part of this trial, but patients will be counseled to continue on their usual diet at home. In addition, only patients who have been stable in weight (e.g., having had a stable weight at home of less than $\pm 5\%$ a change in weight over the last 2 months) will be included in the study.

Study participants should not initiate rigorous exercise routines while on study, but will be encouraged to do activities consistent with a healthy lifestyle (i.e.: walking).

6.4.13. Adverse Events

Each patient must be carefully monitored for the development of any adverse events throughout the study from Screening through the Final Study Visit. This information should be obtained in the form of non-leading questions (e.g., "How are you feeling?"), and from signs and symptoms detected during each examination, from laboratory evaluation, observations of study personnel, and spontaneous reports from patients.

All AEs, including injection site reactions and potential systemic reactions will be graded using the National Cancer Institute Common Terminology Criteria for Adverse Events (CTCAE) grading system. Only injection site reactions considered clinically significant by the Investigator will be recorded as AEs.

Complete details on adverse event monitoring are provided in [Section 7.1](#).

6.4.14. Order of Assessments

When scheduled at the same time point, the order of procedures should be as follows: obtain vital signs, perform 12-lead ECG, followed by blood draws (at the specified time point, if applicable). Adjustments may be made depending upon specific circumstances.

6.5. Pharmacokinetic Measurements

6.5.1. Sample Collection Schedule

Blood samples for PK analysis are to be drawn according to the SOA ([Table 6-1](#)). Plasma will be harvested from these samples and analyzed for RM-493 concentration. The site will be provided with separate instructions for sample processing and shipment.

All patients will have a blood sample collected for PK analysis before study drug is administered on Day 1 and within 5 minutes before study drug is administered on Day 42 and Day 70. The actual (clock) time each PK blood sample is collected will be recorded in the source documents and CRF. For the blood samples on Day 42 and Day 70, the actual time of the previous day's drug injection, as provided by the patient or caregiver, will also be recorded. Patients providing samples for the PK substudy (see next paragraph) do not need to provide a blood sample on Day 70.

Patients participating in the optional PK substudy (anticipated to be up to ~N=8) will have blood samples collected over 24 hours starting on any day from Day 63 through 69 (the second week of the optional, active-dose extension). Blood samples will be collected at 0 (within 5 minutes before dosing), 1, 2, 4, 6, 7, 8, 9, 10, 12, and 24 hours after dosing. The samples collected at 1 and 2 hours will be collected within 5 minutes of the scheduled time; the samples at 4 to 12 hours will be collected within 10 minutes of the scheduled time, and the 24-hour sample will be collected within 10 minutes BEFORE the next dose of study drug. For each PK sample, the actual collection (clock) time will be recorded.

7. ADVERSE EVENTS

Monitoring of adverse events will be conducted throughout the study. Adverse events will be recorded in the CRFs from Screening through the Final Study Visit. Adverse events that occur after the start of study drug administration will be considered treatment emergent adverse events (TEAEs). SAEs will be recorded through the Final Study Visit. All adverse events should be monitored until they are resolved or are clearly determined to be due to a patient's stable or chronic condition or intercurrent illness(es).

7.1. Definitions, Documentation, and Reporting

An **adverse event (AE)** is any untoward medical occurrence associated with the use of a drug in humans, whether or not considered drug related. An adverse event (also referred to as an adverse experience) can be any unfavorable and unintended sign (e.g., an abnormal laboratory finding), symptom, or disease temporally associated with the use of a drug, without any judgment about causality. An adverse event can arise from any use of the drug (e.g., off-label use, use in combination with another drug) and from any route of administration, formulation, or dose, including an overdose.

An adverse event or suspected adverse reaction is considered serious (SAE) if, in the view of either the investigator or sponsor, it results in any of the following outcomes:

- Death.
- Life-threatening. Life-threatening means that the patient was at immediate risk of death from the reaction as it occurred, i.e., it does not include a reaction which hypothetically might have caused death had it occurred in a more severe form.
- In-patient hospitalization or prolongation of existing hospitalization. Hospitalization admissions and/or surgical operations scheduled to occur during the study period, but planned prior to study entry, are not considered AEs if the illness or disease existed before the patient was enrolled in the study, provided that it did not deteriorate in an unexpected manner during the study (e.g., surgery performed earlier than planned).
- A persistent or significant incapacity or substantial disruption of the ability to conduct normal life functions.
- Congenital anomaly/birth defect.
- Important medical event. An important medical event is an event that may not result in death, be life-threatening, or require hospitalization but may be considered an SAE when, based upon appropriate medical judgment, it may jeopardize the patient or patient and may require medical or surgical intervention to prevent one of the outcomes listed in the definitions for SAEs. Examples of such medical events include allergic bronchospasm requiring intensive treatment in an emergency room or at home, blood dyscrasias or convulsions that do not result in in-patient hospitalization, or the development of drug dependency or drug abuse.

7.2. Procedures for AE and SAE Reporting

Each patient must be carefully monitored for the development of any adverse events. This information should be obtained in the form of non-leading questions (e.g., "How are you feeling?") and from signs and symptoms detected during each examination, observations of study personnel, and spontaneous reports from patients.

All adverse events (serious and non-serious) spontaneously reported by the patient and/or in response to an open question from study personnel or revealed by observation, physical examination or other diagnostic procedures will be recorded on the appropriate page of the CRF. Any clinically relevant deterioration in laboratory assessments or other clinical findings is considered an adverse event and must be recorded on the appropriate pages of the CRF. When possible, signs and symptoms indicating a common underlying pathology should be noted as one comprehensive event.

All SAEs that occur during the course of the study must be reported by the investigator to the Medical Monitor **within 24 hours** from the point in time when the investigator becomes aware of the SAE. All SAEs must be reported whether or not considered causally related to the study drug. SAE forms will be completed and the information collected will include patient number, a narrative description of the event and an assessment by the investigator as to the severity of the event and relatedness to study drug. Follow-up information on the SAE may be requested by Rhythm or its designee.

[REDACTED]
Rhythm Pharmaceuticals, Inc.
[name]
[name]
[REDACTED]

All SAE correspondence should be addressed to [REDACTED] for tracking and documentation purposes.

If there are serious, unexpected adverse drug reactions associated with the use of the study drug, Rhythm or designee will notify the appropriate regulatory agency(ies) and all participating investigators on an expedited basis. It is the responsibility of the investigator to promptly notify the Institutional Review Board (IRB)/Independent Ethics Committee (IEC) where required of the IRB/IEC of all unexpected serious adverse drug reactions involving risk to human patients. An unexpected event is one that is not reported in the Investigational Drug Brochure.

For both serious and non-serious adverse events, the Investigator must determine both the intensity of the event and the relationship of the event to study drug administration. Only those injection site reactions considered clinically significant by the Investigator will be recorded as AEs.

Intensity of all AEs including clinically significant treatment-emergent laboratory abnormalities, injection site reactions and potential systemic reactions will be graded according to the CTCAE Version 4.0. The CTCAE grade refers to the severity of the AE and ranges from Grade 1 (mild AE), Grade 2 (moderate AE), Grade 3 (severe AE) and Grade 4 (life-threatening or disabling AE) to Grade 5 (death related to AE).

Adverse events not listed by the CTCAE will be graded as follows:

Mild: discomfort noticed but no disruption of normal daily activity.

Moderate: discomfort sufficient to reduce or affect daily activity.

Severe: inability to work or perform normal daily activity.

Life threatening: represents an immediate threat to life.

Relationship to study drug administration will be determined by the investigator according to the following criteria.

None: No relationship between the event and the administration of study drug. The event is related to other etiologies, such as concomitant medications or patient's clinical state.

Unlikely: The current state of knowledge indicates that a relationship to study drug is unlikely or the temporal relationship is such that study drug would not have had any reasonable association with the observed event.

Possible: A reaction that follows a plausible temporal sequence from administration of the study drug and follows a known response pattern to the suspected study drug. The reaction might have been produced by the patient's clinical state or other modes of therapy administered to the patient.

Probable: A reaction that follows a plausible temporal sequence from administration of the study drug and follows a known response pattern to the suspected study drug. The reaction cannot be reasonably explained by the known characteristics of the patient's clinical state or other modes of therapy administered to the patient.

For the purpose of safety analyses, all AEs that are classified as possible or probable will be considered treatment-related events.

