7.3. Adverse Events and Risks

Overall, RM-493 has been generally well tolerated in previous studies. Drug-Related TEAEs (for which the adverse event was assessed as possibly or probably related to study drug by the investigator) were reported in 19 of 22 (86.4%) subjects who received RM-493 and 6 of 26 (23.1%) subjects who received placebo. Below we have listed other known side effects of RM-493. Because very few studies have been done using RM-493, there may be other unknown side effects. The PIs (or a covering clinician) will be available at all times to study participants in the event of a clinical emergency. Both this availability and how to reach the investigators in an emergency will be clearly communicated orally and in writing to study participants. All study interventions will be provided free of cost.

The following side effects were fairly common with RM-493 treatment and are usually mild:

- Decreased appetite
- Nausea
- Diarrhea
- Skin discoloration/darkening
- Penile erection in males/genital discomfort and sexual arousal in females
- Vertigo
- Dry mouth
- Headache

Side effects that are less common, but could require medical attention include:

- Vomiting
- Nightmares
- Nipple disorder (rare)
- Dermal cyst (rare)

Side effects that are rare but serious include

- Anorexia
- Significant genital discomfort in females (very rare)
- Depression or sad mood (very rare)

Side effects that have not been seen in clinical trials, but will be carefully assessed in the study (see below, [Section 7.5 Guidelines for Additional Evaluations and Suspension of Dosing for a Patient](#)):

- Prolonged erections in males (>4 hours)
- Significant increases in Liver Function tests
- Cancerous changes in skin lesions

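### Protocol 7.2 makes a known response pattern a condition of both causality grades that count as treatment-related, so a new, well-timed reaction to RM-493 has no grade that fits it

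*Protocol*

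**What the plan says.** Protocol 7.2 has the investigator place every adverse event in one of four causality categories.

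- *Possible* and *Probable* share their first sentence: "A reaction that follows a plausible temporal sequence from administration of the study drug and follows a known response pattern to the suspected study drug".
- *Possible* then adds: "The reaction might have been produced by the patient's clinical state or other modes of therapy administered to the patient".
- *Probable* adds the opposite: "The reaction cannot be reasonably explained by the known characteristics of the patient's clinical state", nor by other therapy.
- *Unlikely* applies when "The current state of knowledge indicates that a relationship to study drug is unlikely", or when the timing does not fit.
- *None* applies when there is no relationship. It adds: "The event is related to other etiologies, such as concomitant medications or patient's clinical state".

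The same section then sets the counting rule: "For the purpose of safety analyses, all AEs that are classified as possible or probable will be considered treatment-related events".

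On reporting, Protocol 7.2 sends all SAEs to the Medical Monitor within 24 hours regardless of causality. It provides expedited notice for serious, unexpected adverse drug reactions and defines the middle term: "An unexpected event is one that is not reported in the Investigational Drug Brochure".

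Protocol 7.3 says of the drug: "Because very few studies have been done using RM-493, there may be other unknown side effects". It also names effects not yet seen in trials that this study will watch for, among them significant liver-test increases. The SAP gives no other definition of relatedness.

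**The concern.** The first sentence of *Possible* and *Probable* joins two conditions, timing and a known pattern, and both must hold. The second depends on what was known about RM-493 before the event. A reaction that is new, well timed and without another explanation is the case a causality scale in an early trial most needs to capture. Here it cannot meet the definition of treatment-related.

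The setting makes this more than a drafting detail. Safety and tolerability is the first primary objective (Protocol 2.1.1). Most earlier clinical exposure was by continuous infusion (Protocol 1.3.3), whereas this trial uses a new lipid-based once-daily injection (Protocol 1.3.3.3) in patients with PWS, and a 2.5 mg dose was added after the interim analysis (Protocol 3.4).

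At stake are the accuracy of the investigator's grade, of the relationship column in the by-patient listing (Protocol 8.5), and of any count of treatment-related events. There is also a possible conflict with expedited notice, which looks for drug reactions that are not in the brochure.

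**Working it through.** No sample-size or power figure enters this point. The check sets the four definitions against the three elements they use: plausible timing (T), known response pattern (K), and a possible alternative explanation (A). All inputs are from Protocol 7.2.

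| T | K | A | Category that fits | Treatment-related? |
|---|---|---|---|---|
| yes | yes | yes | *Possible* | yes |
| yes | yes | no | *Probable* | yes |
| yes | no | yes | *None* if the other cause is judged the actual one; otherwise no category | definition not met |
| yes | no | no | no category | definition not met |
| no | yes | yes | *Unlikely* (timing), or *None* | no |
| no | yes | no | *Unlikely* (timing) | no |
| no | no | yes | *Unlikely* (timing), or *None* | no |
| no | no | no | *Unlikely* (timing) | no |

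1. Of the 2 × 2 × 2 = 8 combinations, 2 reach a treatment-related grade, and both need K. None of the 4 combinations without K does.
2. The fourth row is the strongest new signal: good timing and no other explanation. *Unlikely* would need knowledge pointing away from the drug, and having no knowledge is not the same thing. *None* would need a finding of no relationship, and its text points to another cause. The event is left without a category.
3. No element of the scale uses frequency, imbalance against placebo, or the course of the event after stopping or restarting the drug. The text therefore offers no other route to a related grade.
4. A concrete case: Protocol 7.3 lists significant liver-test increases as not yet seen in trials, and Protocol 11.10 reports no signal in the Phase 1/2 studies or in toxicology. A liver-test rise caused by RM-493 would have no pattern to match. Prolonged erection is a weaker example, because Protocol 7.3 lists erections as a fairly common effect and Protocol 11.9 ties them to MC4R agonism, so an investigator could call that a known pattern.
5. Expedited notice: if the word reaction in that rule is read through this scale, the trigger becomes serious, matching a known pattern, and absent from the brochure. These conditions can hold together, since an unlisted event may still fit a known pattern. For a genuinely new reaction they cannot.
6. Where relatedness enters the output: Protocol 8.5 puts it in a by-patient listing. The AE summaries in Protocol 8.5 and SAP 4.8.1 count events by system organ class and preferred term. SAP 4.8.1 adds severity and period. None of them filters on relatedness.
7. Why a related count still matters: the headline safety figure in Protocol 7.3 is of this type. It reports possibly or probably related events in 19/22 = 86.4% on RM-493 and 6/26 = 23.1% on placebo, and both percentages reproduce. A similar figure from this trial, built on the written rule, would leave out or misplace new reactions.

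**The case against.** The strongest reply is that the safety evaluation does not rest on this scale. Events are compared by frequency and severity (Protocol 2.2), and the incidence tables are unfiltered. Every SAE reaches the Medical Monitor with a narrative. Protocol 7.3.1 adds that unanticipated problems involving risk go to the FDA, and the safety committee reviews blinded listings at least monthly (Protocol 3.6). The liver guidance in Protocol 11.10 does not depend on the relatedness grade. All of this stands, and it limits the consequence.

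A reader might infer that the trial cannot detect unknown side effects. The documents do not support that, because a new reaction would appear by arm in the TEAE and SAE tables.

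A reader might also infer that a new reaction is certain never to be counted as related, at any rate of occurrence. That goes too far as well. The text leaves such an event unclassified and does not send it by default to *Unlikely* or *None*. The investigator must still choose, may depart from the wording, and nothing prevents repeated cases from coming to be seen as a known pattern. The result is undefined, and no probability can be attached to it.

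Third, a reader might infer that the rule blocks expedited reporting. Protocol 7.2 ties the two-grade rule to the safety analyses and does not say that the sponsor's expedited decision uses this scale. What remains there is a tension to be clarified.

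The reply does not remove the gap itself. None of these safeguards supplies a category for a new, well-timed event.

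**Conclusion.** The concern holds as a defect in the causality definitions. Read literally, a new reaction with plausible timing and no precedent with RM-493 fits none of the four categories and cannot meet the definition of treatment-related, in a protocol that itself expects that unknown side effects may exist.

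Its reach is limited to the investigator's grading, the relationship entry in the by-patient listing, any treatment-related count, and a possible tension with the expedited-notice wording. The planned incidence tables and the transmission of SAEs are unaffected.

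The conclusion assumes that the known-pattern phrase, which the protocol does not define, means a pattern already established for RM-493. A broader reading that took in class effects would narrow the gap, but would not close it for a reaction new to the class. The documents show no event that was graded down for this reason, so how often it has happened is unknown. The point is worth correcting because the change is small and safety is the first primary objective.

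**What to change.** In Protocol 7.2:

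- Remove the known-pattern condition from *Possible*, so that plausible timing with a possible drug cause is enough.
- In *Probable*, keep a known pattern as a factor that supports the grade but is not required for it.
- State that lack of precedent, or absence from the brochure, is not by itself a reason to grade an event *Unlikely* or *None*.
- State whether the expedited-notice decision uses this scale, so that the definition of unexpected and the definition of related can be read together.

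Check the events already recorded for any graded down on that ground alone. This is best done before unblinding, with the first grade kept alongside the revised one.

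The cost is a few words in one section, matching changes to any CRF instructions that repeat the definitions (these are not in the documents, so this is an assumption), and the check of recorded events. No dose, visit, endpoint or sample size changes. The downside is that somewhat more events will be classed as treatment-related, in the active and placebo arms.
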